### 10.1 Overview of Study Design

This is a multi-center, prospective, post-market study to assess the safety and performance of marketed BD NRFit™ Spinal Needles, the BD Spinal Introducer NRFit™ Needles, the BD Spinal NRFit™ Needle Sets, and the BD Syringes NRFit™.

### 10.2 Sample Size Considerations

The planned sample size is approximately 150 subjects treated with BD NRFit™ Spinal Needle and BD NRFit™ Syringe, and approximately 100 subjects treated with BD NRFit™ Spinal Introducer. The sample size is based on the precision of endpoint estimates as well as the ability to detect adverse events. For a given endpoint with 90% rate, a sample size of 150 would lead to a precision of 4.8%, a sample size of 100 would lead to a precision of 6.0%. Table 1 below contains further detail. For an adverse event with 1% rate, there is a probability of 77.9% to observe at least 1 event in a sample of 150.

Table 1: Sample Size and Precision

Sample Size	Rate	Precision (Half width of 95% CI)
150	90%	4.8%
100	90%	6.0%
150	80%	6.4%
150	3%	3.1%
150	2%	2.7%

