## 4 STUDY DESIGN

### 4.1 Overall Design

This is a multi-center, prospective, open label, single arm post-market study that will enroll approximately 180 participants in order to have a minimum of 150 treated participants who will receive a spinal anesthesia procedure as part of their routine medical care. A minimum of 50 participants for each of the two needle tip types (Quincke and Whitacre tip) will be enrolled in the study. Data related to the safety and performance of the BD Spinal NRFit™ Needles, the BD Spinal Introducer NRFit™ Needles, the BD Spinal NRFit™ Needle Sets, the BD Syringes NRFit™ and ancillary devices will be captured when used as intended.

Participants will be screened against eligibility criteria and will be considered enrolled once the informed consent document is signed. The procedure(s) performed, and device(s) used, will be left to the discretion of the participant's physician investigator.

Participants will be followed from the time of spinal procedure for up to 10 days ( $\pm$  3 days) post spinal procedure to assess for any adverse events/complications. If the participant has been discharged from the hospital prior to day-10 ( $\pm$  3 days) post procedure, follow-up may be performed in a variety of ways including by telephone. The site staff must take advantage of the time window of  $\pm$  3 days only when the 10-day post-procedure occurs during the weekends or holidays. However, any adverse event or complication must be diagnosed and confirmed by a study physician.

Additionally, to assess overall ease of spinal procedure, the clinician performing the procedure will complete a brief survey describing their experience with the procedure.

The total duration of the study is expected to be approximately 49-51 weeks from first participant enrolled up to last participant having last visit.

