### 5.1 Inclusion Criteria

In order to be eligible to participate in this study, an individual must meet all of the following criteria:

1. Any patient, regardless of age or gender, for which the investigator has decided that a neuraxial procedure must be performed utilizing BD NRFit™ Spinal Needles, NRFit™ Spinal Introducer Needles, and NRFit™ Syringes as part of their routine medical care.
2. Expected to be available for observation through the study period (10 days,  $\pm$  3 days, post procedure\*).
3. Able and willing to provide signed and dated informed consent or legal authorized representative (LAR) authorized to give consent on behalf of the participant (Note: Consent of guardian or parent may be required for participants under the age of 18 years; participant assent may be required as well).

\*The time window of  $\pm$  3 days must be used when the 10-day post-procedure occurs during the weekends or holidays.

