# 6 STUDY INTERVENTIONS

## 6.1 Investigational/Test Device

The BD Spinal NRFit™ Needles (BD Quincke Spinal NRFit™ Needle and BD Whitacre Spinal NRFit™ Needle) are intended to gain entry into or puncture the spinal cavity permitting injection (including anesthesia) / withdrawal of fluids for purposes of diagnostic lumbar puncture and myelography procedures. They consist of a needle, stylet, and needle shield and are available in various gauges and needle lengths. The needle consists of a hollow needle (cannula) bonded to a translucent hub at one end and a specific needle point type (Quincke or Whitacre) at the other end. The stylet has a handle which is color coded and correlates to the gauge size.

The BD Spinal Introducer NRFit™ Needle is intended for placement or introduction of spinal needles. The BD Spinal Introducer NRFit™ Needle consists of a needle, needle hub and needle shield and is available in various gauges. The needle consists of a hollow needle (cannula) bonded to a translucent colored hub (per gauge) at one end and a specific needle point type at the other end. The introducer needle is an optional aid through which a spinal needle can be inserted.

The needle hub of the BD Spinal NRFit™ Needles and the BD Spinal Introducer NRFit™ Needle incorporates ISO 80369-6 compliant connectors. The needle shields are yellow to

indicate that the devices are intended to only connect to ISO 80369-6 (NRFit™) compatible devices such as syringes.

The BD Spinal NRFit™ Needles and the BD Spinal Introducer NRFit™ Needle are sterile, non-toxic and non-pyrogenic. These products are not made with natural rubber latex, Bisphenol A (BPA) or Di-ethylhexyl Phthalate (DEHP).

The BD Spinal NRFit™ Needles and the BD Spinal Introducer NRFit™ Needle are to be used by properly qualified and trained healthcare professionals.

The BD Spinal NRFit™ Needle Sets (BD Quincke Spinal NRFit™ Needle Set and BD Whitacre Spinal NRFit™ Needle Set) consist of either a BD Quincke Spinal NRFit™ Needle or a BD Whitacre Spinal NRFit™ Needle and a BD Spinal Introducer NRFit™ Needle. The indications for use, populations for which the devices are intended, and materials remain the same of those for the BD Spinal NRFit™ Needles and the BD Spinal Introducers NRFit™ Needles.

The BD Syringes NRFit™ (BD Syringe NRFit™ Lok and BD Syringe NRFit™ Slip) are intended for transient use, intended for neuraxial use by healthcare professionals for aspiration/injection of fluids.

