### 7.3 Spinal procedure

Choice of the specific BD Spinal NRFit™ Needle, gauge, length, tip, type and size of a BD Syringes NRFit as well as the option of using a BD Spinal NRFit™ Needle set and BD Spinal Introducer NRFit™ Needle, required for an individual participant is left to the discretion of the clinician. BD Spinal Introducer NRFit™ Needle sizes paired to selected BD Spinal NRFit™ Needles may be used. The devices, participant, aseptic technique, and insertion site will be prepared according to standard medical practices and site-specific procedures.

Ancillary devices are the BD Blunt Fill NRFit™ Needles and the BD Blunt Filter NRFit™ Needles, and they are used to aspirate desired medication from an ampule or vial by connecting the needle hub to a NRFit™ syringe, and to dose into a BD Syringes NRFit™.

If a BD Spinal Introducer NRFit™ Needle is used, it is placed between the lumbar vertebrae at the desired interspace and angle. The BD Spinal NRFit™ needle (Quincke or Whitacre) is then inserted through the Introducer NRFit™ needle. The stylet is removed to check for the appearance of Cerebrospinal Fluid (CSF), and then replaced if further advancement of the spinal needle is needed.

Once the BD Spinal NRFit™ Needle and BD Spinal Introducer NRFit™ Needle, if the latter is used, is successfully placed, the procedure will be completed, injecting the medication through a BD Syringes NRFit™ into the CSF, and removing the NRFit™ spinal and introducer needles.

The devices will be utilized according to the specific medical needs of the participant and site-specific protocols and procedures.

Residents in training program in anesthesia cannot perform the spinal procedure within the study.

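### The plan counts on about 100 introducer participants, but no enrolment rule secures that number, and the stated 6.0% half-width is not the one the planned exact interval gives

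*Protocol*

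**What the plan says.** Protocol 10.2 plans about 150 participants treated with the spinal needle and syringe, and "approximately 100 subjects treated with BD NRFit™ Spinal Introducer". It adds that "a sample size of 100 would lead to a precision of 6.0" percent at a 90% rate. SAP 2.4 repeats both figures. The endpoint they serve, placement success when an introducer is used, is one of the four primary performance endpoints in Protocol section 3 and SAP 1.2.

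The enrolment rules are these:

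- Total: about 180 enrolled "in order to have a minimum of 150 treated participants" (Protocol 4.1).
- Tip type: "A minimum of 50 participants for each of the two needle tip types" (Protocol 4.1).
- Site: no site may contribute more than 25% of participants (Protocol synopsis, Investigational Sites).

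On the introducer itself, Protocol 6.1 says: "The introducer needle is an optional aid through which a spinal needle can be inserted". Protocol 7.3 says that the choice of needle and syringe, and the option of an introducer or a needle set, "required for an individual participant is left to the discretion of the clinician". Protocol 7.3.1 records introducer details only where one was used. Inclusion criterion 1 reads differently. It describes a procedure performed "utilizing BD NRFit™ Spinal Needles, NRFit™ Spinal Introducer Needles, and NRFit™ Syringes as part of their routine medical care".

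Protocol 10.5.1.1 and SAP 5.2.1.1 place a participant in the introducer population if an introducer was used at the last attempt, and both specify an exact 95% interval. The SAP denominator is treated participants using the introducer.

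**The concern.** The size of one primary endpoint's denominator depends on a choice made case by case. The plan neither predicts how often that choice will go towards an introducer nor sets a minimum. Tip type is also left to the clinician, yet it has a floor, so the protocol does set device minimums where it wants them without dictating individual choices. Enrolment could close with 150 treated and both tip-type floors met, but well under 100 in the introducer population. The last-attempt rule can lower the count further, because a participant who starts with an introducer and finishes without one drops out.

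The result would be a primary performance estimate less precise than the plan states, with nothing during enrolment to signal it. The 6.0% also needs checking in its own right, because the planned interval is exact and that figure may not be.

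**Working it through.** **Inputs.** From Protocol 10.2 and SAP 2.4: introducer n = 100, rate 90%, half-width 6.0%. From Protocol 4.1: at least 150 treated. From Protocol 10.5.1.1 and SAP 5.2.1.1: exact (Clopper-Pearson) 95% interval. Not in the documents, so assumed here: the share of participants using an introducer (50% to 75% shown) and the shortfall counts of 75 and 50 users.

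**1. Reproduce the stated figure.** With p = 0.90, n = 100 and z = 1.96:

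- Wald: 1.96 × √(0.9 × 0.1 / 100) = 5.88%.
- Wilson: z√(p(1−p)/n + z²/4n²) / (1 + z²/n) = 5.96%, which rounds to the stated 6.0%.
- Exact: with x = 90, the limits are the 2.5% quantile of Beta(x, n−x+1) and the 97.5% quantile of Beta(x+1, n−x), that is 82.4% and 95.1%. The half-width is (95.10 − 82.38)/2 = 6.36%.

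So 6.0% matches a Wilson interval. The planned method gives 6.4%.

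**2. Half-width by number of introducer users, at a 90% rate.**

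| Users | Share of 150 | Wilson | Exact |
|---|---|---|---|
| 50 | 33% | 8.5% | 9.2% |
| 75 | 50% | 6.9% | 7.4% |
| 100 | 67% | 6.0% | 6.4% |
| 110 | 73% | 5.7% | 6.04% |
| 112 | 75% | 5.6% | 5.99% |
| 150 | 100% | 4.8% | 5.1% |

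Where 90% of n is not a whole number, the formula was evaluated at the fractional count. On the exact method, about 112 users are needed for 6.0%.

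**3. Separate the two effects.** Moving from 6.0% to 6.4% at 100 users is purely the interval method. The effect of a shortfall, with the method held at exact, is 6.4% to 7.4% for 75 users (1.0 point) and 6.4% to 9.2% for 50 users (2.8 points).

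**4. Chance of reaching 100.** The share needed is 100/150 = 66.7%. Let X be the number of users among 150 treated, with X ~ Binomial(150, s), where s is the usage share and participants are independent. Then P(X ≥ 100) is:

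| Assumed usage s | Expected users | P(X ≥ 100) |
|---|---|---|
| 50% | 75 | below 0.1% |
| 60% | 90 | 5.6% |
| 66.7% | 100 | 53.8% |
| 70% | 105 | 83.7% |
| 75% | 112.5 | 99.1% |

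The outcome moves from unlikely to near certain between 60% and 75% use, and the plan gives no value for that share. Independence is a simplification: usage habits probably cluster by site, which would spread X more widely than the binomial does.

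**The case against.** The best defence is that the number is planned. Protocol 10.2 names about 100 introducer participants as a target, the sponsor supplies introducers and needle sets, and seven catalogue items in Appendix 16.1 are needle-plus-introducer sets. The 6.0% is worded conditionally, as what 100 participants would give. The study estimates rates and tests no hypothesis, and the SAP would report the introducer denominator with its exact interval, so a shortfall would be visible in the results. All of this stands. It means that a safeguard during enrolment is missing, not that the endpoint was left unplanned. It does not supply a rule that makes the target happen, and it does not make 6.0% the exact half-width.

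A reader might infer three stronger conclusions that the documents do not support:

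- **That the study will fall well short of 100.** No usage rate is given, and at 75% use the target is very likely met.
- **That the protocol commits to conflicting introducer numbers because inclusion criterion 1 requires one for everyone.** Read literally, the criterion does say so. But sections 6.1, 7.3 and 7.3.1 make use optional, and section 2.3 speaks of participants needing one of the study devices. The criterion is better read as a list of the device family. Its wording deserves tidying, but a planned 100 and clinician discretion can coexist.
- **That a shortfall materially raises the chance of wrongly meeting the 90% placement criterion.** Neither document states that this criterion is applied separately to the introducer group. Even if it were, with an assumed true rate of 85% the chance of observing at least 90% is 9.9% with 100 users and 10.8% with 75. It reaches 21.9% only at 50.

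**Conclusion.** The point holds as a moderate one that should be corrected. The plan states a size and a precision for a primary endpoint, and no enrolment rule secures the size. Whether 100 is reached depends on introducer use being roughly two thirds or more, a quantity the plan neither states nor controls. The loss, if it occurs, is one of precision: an exact half-width of 7.4% at 75 users or 9.2% at 50, against 6.4% at 100. Those two counts, the usage shares and independence between participants are assumptions made here.

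The mismatch between 6.0% and the planned exact method needs no such assumption. It is a difference of 0.4 points at the planned 100 users and holds however many introducers are used.

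**What to change.** Either of two changes is enough.

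1. **Restate the precision.** In Protocol Table 1 and SAP Table 2, and in the sentence above each, replace the 6.0% entry with exact half-widths for 50, 75 and 100 introducer users (9.2%, 7.4% and 6.4%). State that the number of introducer users is not controlled. This is a text change with no operational cost; the price is a less favourable stated figure.
2. **Add a floor.** Require about 100 participants with an introducer used at the last attempt, alongside the tip-type floors. Counting at the last attempt makes the floor match the analysis population in Protocol 10.5.1.1 and SAP 5.2.1.1; a count of anyone ever treated with an introducer would not. Track it in the EDC and meet it through site mix within the 25% per-site cap, leaving each participant's device choice unchanged. The cost is one tracking rule and a small risk of slower enrolment. The 6.0% entry should still become 6.4%.

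In either case, as a minor clarification, reconcile inclusion criterion 1 with the sections that describe the introducer as optional.

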### 10.3 Analysis Population

The following populations are defined:

Population	Description
Enrolled	All participants who sign the ICF
Treated	All participants in whom a spinal anesthesia procedure is attempted, regardless of success
Safety	All participants in whom a spinal anesthesia procedure is successful

The primary performance endpoints analysis will be performed on the treated population. The primary safety endpoint analysis for PDPH incidence will be performed on the safety population. The primary safety endpoint analysis for device/procedure-related adverse events (other than PDPH) will be performed on the treated population.

## 10.4 General Considerations

Study endpoints may be missing due to reasons including lost to follow-up visits, procedures not being performed, or participant discontinuation. It is essential to minimize missing data and always record why it is missing. Analyses will be performed using evaluable data, combining all investigational sites. Statistical output will be generated using SAS (SAS Institute, Cary, NC) version 9.4 or above.

## 10.5 Primary Endpoint(s)

### 10.5.1 Primary Performance Endpoints

#### 10.5.1.1 Performance of the BD Spinal NRFit™ Needle and BD NRFit™ Introducer

- Rate of successful BD Spinal NRFit™ Needle placement

The successful placement of the BD Spinal NRFit™ needle in the subarachnoid location is defined as the spontaneous appearance of cerebrospinal fluid (CSF) emerging from the spinal needle hub. In case of multiple attempts, successful placement is determined by the last attempt.

- Rate of successful BD Spinal NRFit™ Needle placement when a BD Spinal NRFit™ Introducer is used

The successful placement of the BD Spinal NRFit™ needle in the subarachnoid location is defined as the spontaneous appearance of cerebrospinal fluid (CSF) emerging from the spinal needle hub for subjects who used BD NRFit™ introducer. In case of multiple attempts, successful placement is determined by the last attempt. If a subject uses BD NRFit™ introducer for the last attempt, the subject will be considered as part of the introducer population.

The incidence rate for the primary performance endpoints will be calculated as the number of participants experiencing the event divided by the total number of treated participants; 95% confidence interval (exact method) will be calculated.

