5.2 Analysis Methods

5.2.1 Primary Performance Endpoints

5.2.1.1 Performance of the BD Spinal NRFit™ Needle and BD NRFit™ Introducer

- Rate of successful BD Spinal NRFit™ Needle placement

The successful placement of the BD Spinal NRFit™ needle in the subarachnoid location is defined as the spontaneous appearance of cerebrospinal fluid (CSF) emerging from the spinal needle hub. In case of multiple attempts, successful placement is determined by the last attempt.

It will be computed as the number of participants experiencing the event divided by the total number of subjects with needles attempted; 95% confidence interval (exact method) will be calculated. The analysis will be performed on the treated population as defined in section 4.1.

The incidence of successful needle placement will be based on counts of "Yes" response to the following question on the "Spinal Procedure Details - BD NRFit Needle" CRF page: "Was there a spontaneous appearance of cerebrospinal fluid (CSF) emerging from the needle hub?"

- Rate of successful BD Spinal NRFit™ Needle placement when a BD Spinal NRFit™ Introducer is used

The successful placement of the BD Spinal NRFit™ needle in the subarachnoid location is defined as the spontaneous appearance of cerebrospinal fluid (CSF) emerging from the spinal needle hub for subjects who used BD NRFit™ introducer. In case of multiple attempts, successful placement is determined by the last attempt. If a subject uses BD NRFit™ introducer for the last attempt, the subject will be considered as part of the introducer population.

The incidence rate for the primary performance endpoints will be calculated as the number of participants experiencing the event divided by the total number of treated participants using BD NRFit™ introducer; 95% confidence interval (exact method) will be calculated.

A subject will be included in the analysis population if both of the following two conditions are met:

- Spinal Procedure CRF page: 'Was spinal procedure performed or attempted using BD NRFit devices?' Equals 'Yes'

THIS SUBJECT MATTER IS RESTRICTED SOLELY FOR THE USE OF BECTON DICKINSON AND COMPANY AND ITS SUBSIDIARIES

 BD	Statistical Analysis Plan	Page No.
	Study ID: MDS-21NRFit001	8 of 13

GFM-10082C

- AND

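### Protocol 10.5.1.1 gives the introducer placement endpoint the wrong denominator (all treated participants); SAP 5.2.1.1 uses introducer users, and the protocol text should be aligned with it

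*Protocol*

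**What the plan says.** Protocol 10.5.1.1 describes two primary performance endpoints for the needle. The first is successful placement, shown by spontaneous CSF at the hub. The second is the same event, restricted to CSF "emerging from the spinal needle hub for subjects who used BD NRFit™ introducer". A membership rule follows: "If a subject uses BD NRFit™ introducer for the last attempt, the subject will be considered as part of the introducer population". One closing sentence then sets the rate for the primary performance endpoints, in the plural, as the "number of participants experiencing the event divided by the total number of treated participants", with an exact 95% confidence interval.

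Protocol 10.3 defines treated as "All participants in whom a spinal anesthesia procedure is attempted, regardless of success" and adds: "The primary performance endpoints analysis will be performed on the treated population". The introducer population named in 10.5.1.1 is not in the 10.3 table.

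Protocol 10.2 plans "approximately 150 subjects treated with BD NRFit™ Spinal Needle and BD NRFit™ Syringe" and "approximately 100 subjects treated with BD NRFit™ Spinal Introducer", and quotes a precision of 6.0% for 100 subjects at a 90% rate. Protocol 6.1 describes the introducer as optional, and 7.3 leaves its use to the clinician.

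SAP 5.2.1.1 keeps the same endpoint definition and last-attempt rule, but the number of successes is "divided by the total number of treated participants using BD NRFit™ introducer". It also lists the CRF answers that place a participant in that group.

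Protocol 3.1 expects CSF to appear in at least 90%, in an item that refers to the literature on spinal needles and introducer needles together. SAP 1.3 gives at least 90% for needle placement in general. Neither states a separate limit for the introducer endpoint.

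**The concern.** The second endpoint is conditional on introducer use. If its denominator is every treated participant, each person treated without an introducer lowers the rate exactly as a failed placement would. The result then mixes how often the needle was placed successfully with how often clinicians chose an introducer, and only the first is the stated objective.

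The two documents therefore give two different rates for one primary endpoint from the same data. Anyone checking a reported result against the protocol formula would not reproduce a figure computed under the SAP. The protocol also disagrees with itself: 10.2 attaches a precision to 100 introducer subjects, while 10.5.1.1 divides by all treated, planned at about 150.

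**Working it through.** **Inputs.** Treated participants N = 150 and introducer users m = 100 (Protocol 10.2, both approximate). Interval: two-sided 95%, exact (Protocol 10.5.1.1). Reference level: 90% (Protocol 3.1, SAP 1.3).

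**The plan's own figure first.** Protocol 10.2 gives a half-width of 6.0% for n = 100 at 90%. The Wilson half-width is

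z·√[p(1−p)/n + z²/(4n²)] / (1 + z²/n), with z = 1.96, p = 0.90, n = 100, which gives 5.96%.

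This rounds to 6.0%. The simple normal (Wald) form gives 5.88%. At n = 150 the Wilson form gives 4.84%, matching the stated 4.8%. The 6.0% is therefore a figure for 100 introducer users as the denominator, not for 150 treated.

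**Relation between the two rules.** Let x be the number of introducer users with successful placement.

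- Protocol rule, read literally: x/N
- SAP rule: x/m
- So the protocol rate = SAP rate × m/N, and since x cannot exceed m, its ceiling is m/N.

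**Results.** Exact limits are the 2.5% quantile of Beta(x, n−x+1) and the 97.5% quantile of Beta(x+1, n−x), where n is the denominator used; when x = n the upper limit is 100%.

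| Successes among 100 users | Protocol rule | SAP rule |
|---|---|---|
| 100 | 100/150 = 66.7% (58.5 to 74.1) | 100/100 = 100% (96.4 to 100) |
| 90 | 90/150 = 60.0% (51.7 to 67.9) | 90/100 = 90.0% (82.4 to 95.1) |

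**How far the ceiling depends on introducer use.** With N = 150 and every placement successful:

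| Introducer users | Highest possible protocol rate |
|---|---|
| 75 | 50.0% |
| 100 (planned) | 66.7% |
| 120 | 80.0% |
| 134 | 89.3% |
| 135 | 90.0% |

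If the 90% level is applied to this endpoint, the protocol formula can reach it only when at least 0.90 × 150 = 135 participants use an introducer and, at exactly 135, all placements succeed.

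**The case against.** The strongest reply is that the plan, taken as a whole, already points to introducer users. The endpoint is conditional by name. The last-attempt membership rule has little purpose if everyone treated is counted. Protocol 10.2 gives precision for 100. Protocol section 10 describes itself as a summary that the SAP will set out in more technical detail, and SAP 5.2.1.1 does so with an explicit denominator and CRF conditions. All of this stands: it identifies the intended rule and limits the practical effect. It does not remove the sentence in 10.5.1.1, which names a different denominator.

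It can also be said that Protocol 10.4 restricts analyses to evaluable data, which might exclude participants without an introducer. That paragraph is about missing data. A participant treated without an introducer has no missing value, and the 10.5.1.1 wording is explicit about the total, so this does not override it.

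Three stronger readings are tempting and are not supported:

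- *The introducer endpoint is bound to fail its acceptance criterion even with perfect performance.* Neither document states the 90% limit separately for this endpoint, the 66.7% ceiling rests on two approximate counts, and the SAP formula has no such ceiling.
- *The protocol overrides the SAP, so the SAP rate is invalid.* Neither document states an order of precedence on this point.
- *SAP 4.1 contradicts SAP 5.2.1.1.* It does not. Introducer users are a subset of the treated population, and the first inclusion condition in 5.2.1.1 is the treated-population CRF item itself.

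**Conclusion.** The point holds as an error in one protocol sentence about a primary endpoint. Read literally, Protocol 10.5.1.1 counts participants without an introducer as non-successes. On the planned 100 of 150 this multiplies the rate by two thirds: 60.0% instead of 90.0% when 90 users succeed, and at most 66.7%. These figures assume the planned counts; the factor is m/N and moves with actual introducer use, for which Protocol 10.2 gives only an approximate target.

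The consequence is limited. SAP 5.2.1.1 already carries the intended denominator, and an analysis run under it would be correct. What remains is a protocol formula that does not match the planned analysis or the protocol's own introducer population and precision figure. It is worth correcting so that the protocol and the reported rate agree.

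**What to change.** In Protocol 10.5.1.1, keep the present formula for overall needle placement and give the introducer endpoint its own: the denominator is treated participants in whom a BD NRFit introducer was used, with membership set by the last-attempt rule already in that section. This matches SAP 5.2.1.1. In Protocol 10.3, add a cross-reference saying that the introducer endpoint is analysed in that subset of the treated population. SAP 4.1 needs no change.

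The cost is one sentence and one cross-reference in the protocol. No new data, CRF items or analysis programs are needed, because the SAP already specifies the CRF conditions.
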